### 4.2 Exclusion Criteria

- 4.2.1 Inability to complete written, informed consent.
- 4.2.2 Incarceration at the time of any study visit.
- 4.2.3 Active suicidality, as determined by the patient's HIV provider or social worker following a positive response (1, 2, or 3) to PHQ-9 Item #9 and a positive response (yes) to one or more of the three questions (for Question #3, the previous attempt must be within the past 10 years) on the Patient Suicidality Form (see Appendix).
- 4.2.4 Diagnosed vascular disease (documented history of angina pectoris, coronary disease, peripheral vascular disease, cerebrovascular disease, aortic aneurysm, or otherwise known atherosclerotic disease).
- 4.2.5 History of congestive heart failure, even if currently compensated.
- 4.2.6 Diagnosed disease or process, besides HIV infection, associated with increased systemic inflammation (including, but not limited to, systemic lupus erythematosus, inflammatory bowel diseases, other collagen vascular diseases).

Note: Hepatitis B or C co-infections are NOT exclusionary

- 4.2.7 Known or suspected malignancy requiring systemic treatment within 180 days of the Entry Visit.

NOTE: Localized treatment for skin cancers is not exclusionary.

- 4.2.8 Therapy for serious medical illnesses within 14 days prior to screening.

Note: Therapy for serious medical illnesses that overlaps with a main study visit will result in postponement of that study visit until the course of therapy is completed; postponement outside of the allowed study visit timeframe will result in study discontinuation.

- 4.2.9 Pregnancy or breastfeeding during the course of the study.

- 4.2.10 Receipt of investigational agents, cytotoxic chemotherapy, systemic glucocorticoids (of any dose), or anabolic steroids at the Entry Visit.

Note: Physiologic testosterone replacement therapy or topical steroids is not exclusionary. Inhaled/nasal steroids are not exclusionary as long as the participant is not also receiving HIV protease inhibitors.

- 4.2.11 Active drug use or dependence that, in the opinion of the investigator, would interfere with adherence to study requirements.

- 4.2.12 History of schizophrenia, bipolar disorder, or dementia.

NOTE: Depression is not exclusionary as long as the severity of depression does not impede ability to perform the required study procedures.

- 4.2.13 Musculoskeletal or neurologic disorders that impede ability to perform the required study procedures.

- 4.2.14 History of sleep apnea or restless leg syndrome.

If participants are excluded due to the above criteria, they may be approached again in the future or have their study visit rescheduled within the allowable timeframe if these criteria are no longer applicable.

## 5.0 STUDY TREATMENT

### 5.1 SHUTi

To minimize treatment barriers, attrition, and subject burden, the SHUTi treatment sessions will occur in private at [name] laboratory, the ICRC, the Infectious Diseases Research Clinic at Eskenazi Health Hospital, or a remote location selected by the patient where s/he can access a computer with internet, such as the patient's home, the patient's work, a family member's/friend's home, or a public library. The location will be chosen by the participant. Patients will be provided with ear bud headphones if they plan to use them at remote locations and do not already own a pair of headphones that they would rather use. Up to 6 sessions will be performed between the Entry Visit and the Week 10 Visit. No physiologic or biologic assessments will be performed during these sessions. The participants need not be fasting for these sessions.

At each in-person SHUTi session, a psychology research assistant trained in the use of this intervention will first collect homework and will start the appropriate session on a computer. The patient will then work through the session alone at his/her own pace. At the end of the session, the research assistant will give the patient the printed homework assignment and will schedule the next session.

Remote SHUTi sessions will be scheduled, just like in-person sessions. Patients who select the remote treatment option will be given a SHUTi binder with printouts of all future homeworks at the time of randomization at the Entry Visit. To begin each remote SHUTi session, an assistant will call the patient to instruct the patient to put last week's homework in the SHUTi binder, to address any technical issues, and to ensure that the patient has launched the correct SHUTi session for that day. The patient will then work alone through the SHUTi session at his/her own pace, with the assistant monitoring progress remotely on the secure SHUTi website set up for this trial. To end the session, the assistant will call the patient back to address any questions and ensure that the patient has identified the correct printed homework in the SHUTi binder.

## 5.2 Prohibited Medications

- Investigational agents
- Cytotoxic chemotherapy
- Systemic glucocorticoids (topical steroids are allowed; inhaled/nasal steroids are allowed only if the participant is not also receiving HIV protease inhibitors)
- Anabolic steroids (physiologic testosterone replacement therapy is not exclusionary)

## 6.0 CLINICAL EVALUATIONS

### 6.1 Schedule of Events

Evaluation	Entry Visit for both Study I and Study II (within 90 days of last clinic-based ISI screening and HIV-1 RNA level assessment)	Weekly SHUTi Sessions for the intervention group in Study I (6 sessions in total)	Week 10 Visit for Study I (for both groups; 63-84 days after Entry Visit)
Informed Consent	X		
Documentation of HIV Status	X		
Medical/Psychiatric History	X		
Medication/Supplement Use History	X		
Diagnoses	X		X
Updated Psychiatric Treatment History			X
Updated Medications			X
Updated Diagnoses			X
Height	X		
Weight	X		X
Vital Signs	X		X
Laboratories obtained through routine clinical care	X		
Questionnaires: ISI, PSQI, PHQ-9, SF-36, WHOQOL-HIV, CSRQ-25, GAD-7, PANAS	X		X
Sleep History and Beliefs Survey (PRE-Treatment)	X		
Sleep History and Beliefs Survey (Post-Treatment)			X
Sleep Diary*	X*		X*
Alcohol, tobacco, substance use questionnaires	X		X
FRAIL Scale (frailty assessment)	X		
Fried Index (frailty assessment)	X		
SPPB Physical Functioning Assessment	X		
DSST Dementia Assessment	X		
Randomization for Study I participants	X		
SHUTi Intervention		X	

\*The study team will call the participant 3 days after the Entry Visit to verbally collect the participants first sleep diary. The study team will again call the participant 3 days after the Week 10 Visit to collect the second sleep diary.

## 6.2 Definitions for Schedule of Events – Special Instructions and Definitions of Evaluations

### 6.2.1 Documentation of HIV-1 Infection

HIV-1 infection documentation must be present in the source documentation at the Entry Visit. HIV-1 infection, documented by both: (1) any licensed rapid HIV test or HIV enzyme test kit at any time prior to study entry and (2) by at least one detectable HIV-1 antigen or at least one detectable plasma HIV-1 RNA viral load.

### 6.2.2 Medical/Psychiatric History

A medical/psychiatric history must be present in the source documents. Record the following on CRFs at either the Screening Visit:

- Birthdate
- Sex
- Patient's self-report of ethnicity (Hispanic vs. Non-Hispanic) and race (White, Black, Asian, Native American, Pacific Islander)
- Initial date of HIV infection documentation
- Route of HIV infection (heterosexual contact, same sex contact, injection drug use, blood transfusion)
- Diagnoses (all medical and psychiatric)

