### 1.3 Study II Primary Objectives

1.3.1 To compare FRAIL scale, Fried Index, and SPPB scores between those with ISI scores  $\geq 11$  and those with ISI  $< 11$ .

1.3.2 To compare CSRQ-25 and Digit Symbol Substitution Test (DSST) scores between those with ISI scores  $\geq 11$  and those with ISI  $< 11$ .

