The American College of Physicians has stated that the preferred treatment for chronic insomnia in adults is not pharmacologic therapy but rather cognitive behavioral therapy for insomnia (CBT-I) due to its more significant results in terms of both efficacy and longevity of response (26). In addition, CBT-I is not associated with adverse effects that may complicate therapy with sleep medications (e.g. abuse potential, cognitive impairment, drug interactions with HIV antiretrovirals, accidents). However, providing CBT-I has proven difficult in environments where there are insufficiently trained providers. In addition, patients may not be able to attend dedicated sessions with a CBT-I therapist due to financial or time restraints. To address these issues, an evidence-based, cognitive-behavioral, online intervention for insomnia called Sleep Healthy Using The Internet (SHUTi) was developed by our colleague and consultant, [name]. SHUTi is based on a well-established face-to-face CBT-I (27, 28) and incorporates sleep restriction, stimulus control, sleep hygiene, cognitive restructuring, and relapse prevention. A comparison of CBT-I to insomnia medications revealed that patients receiving CBT-I have similar short-term and better long-term outcomes (29). There is also a preference for and greater acceptance of CBT-I (30). Each SHUTi session has the same structure: the main content, a homework screen with options, and a summary of the main points. The Internet requirements are minimal (SHUTi can run on a dial-up connection). Although SHUTi has proven quite successful in treating insomnia in the general population, *this intervention has not been tested specifically in an HIV-infected population for whom there are unique characteristics and stressors that may influence the response to this intervention*. For example, the previous studies using SHUTi involved primarily white, educationally-advantaged persons as opposed to our local HIV patient population that is majority black and from lower socioeconomic status (SES) backgrounds with a chronic, stigmatizing disease.

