### 3.0 STUDY DESIGN

#### 3.1 Overview

Our objectives will be met by performing two studies. The first is a 10-week, randomized, controlled, single-blinded, two-arm, parallel group, pilot trial at a single center and the second is a cross-sectional two-group comparative study.

Study I: A total of 40 persons with HIV may be screened and consented to identify the 32 participants to be enrolled and randomized into the pilot trial. These participants will be  $\geq 18$  years old, have been receiving antiretroviral therapy for at least three months with an HIV viral load  $< 75$  copies/mL, and have an ISI score  $\geq 11$ . These participants will be randomized 1:1 (stratified by age  $<40$  vs.  $\geq 40$  years) to either insomnia treatment with the SHUTi cognitive behavioral therapy program (N=16) or usual care (N=16).

Study II: The 32 participants with insomnia from Study 1 will then be compared to a similar group of 12 HIV-infected patients but with an ISI score  $< 11$ . Six will be  $<40$  years old and the other six will be  $\geq 40$  years old). Approximately 15 persons with HIV may be screened to identify this second group of 12 participants without insomnia.

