#### 6.2.5.12 Digit Symbol Substitution Test (DSST)

The DSST is a sensitive measure of dementia. The DSST requires that the participant fill in a series of symbols correctly coded within 90 seconds. The higher the score, the better the performance. This test requires a pencil with eraser, stop watch, DSST task sheet, and scoring template (see Appendices). The test will be administered in a quiet environment at a desk or table.

The DSST will only be administered at the Entry Visit.

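### No source of education or socioeconomic status is named, although DSST is a Study II primary outcome compared once between non-randomised groups

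*Combined protocol and SAP*

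**What the plan says.** Section 1.3 makes cognition a primary objective of Study II: "To compare CSRQ-25 and Digit Symbol Substitution Test (DSST) scores between those with ISI scores" at or above 11 and those below 11. Section 6.2.5.12 describes the test as timed ("The DSST requires that the participant fill in a series of symbols correctly coded within 90 seconds") and adds "The DSST will only be administered at the Entry Visit".

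Section 3.1 defines the contrast: "The 32 participants with insomnia from Study 1 will then be compared to a similar group of 12 HIV-infected patients" whose ISI is below 11. Six of the 12 are to be under 40 and six 40 or over. The 32 have no such quota; age only stratifies their randomisation (section 3.3).

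The history items for the CRF are in section 6.2.2, under "Record the following on CRFs at either the Screening Visit". The social and demographic entries are birthdate, sex and "Patient's self-report of ethnicity (Hispanic vs. Non-Hispanic) and race (White, Black, Asian, Native American, Pacific Islander"; the rest are HIV date, HIV route and diagnoses. No education or socioeconomic item is named in 6.2.3, in the Schedule of Events (6.1), or in the descriptions of the questionnaires and sleep surveys (6.2.6.6 and 6.2.6.7). Section 10.2.2 says that medical records will be reviewed for demographics, without itemising them, and its list of what the questionnaires assess does not include education.

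Section 2.2 gives, as an example of why the local response to SHUTi may differ, that "the previous studies using SHUTi involved primarily white, educationally-advantaged persons as opposed to our local HIV patient population that is majority black" and of lower socioeconomic status.

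**The concern.** Study II is observational. Whether a participant is in the group of 32 or the group of 12 depends on ISI score, and nothing in the design equalises schooling between the groups. DSST is taken once, so no within-person change removes a stable trait such as education. If education is related both to the DSST score and to group, the crude difference mixes the two, and a reader of the report would raise this explanation first.

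Section 2.3 says these data are meant to relate insomnia to frailty and cognitive impairment in support of later funding applications, so an interpretable cognition contrast is the purpose of the exercise. Those enrolled only for Study II attend a single visit, so an item not asked then is hard to recover.

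There is also a descriptive loss. The protocol itself names education and socioeconomic status as ways in which its patients differ from earlier SHUTi samples, but names no variable with which to describe them.

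**Working it through.** **The plan's own figures.** Study I: 40 × 0.80 = 32 randomised, 16 per arm, and 16 × 0.75 = 12 completers per arm, as section 9.2 states. Study II: 15 × 0.80 = 12. Total analysed at entry: 32 + 12 = 44. These figures reproduce, and none of them changes if education is added.

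**Precision of the DSST contrast, in SD units.** SE = √(1/32 + 1/12) = √0.1146 = 0.339. By normal approximation:
- the 95% half-width is 1.96 × 0.339 = 0.66 SD;
- the difference detectable with 80% power is about 0.95 SD;
- power at 0.5 SD is 31%.

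**Bias if education is ignored.** The documents give neither the education-DSST correlation r nor the education imbalance d (in SD). Both are assumed: r from 0.2 to 0.5, d from 0.25 to 0.5. Shift b = r × d. Rejection rate with no true difference = 1 − Φ(1.96 − b/SE) + Φ(−1.96 − b/SE).

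| r | d | b (SD) | b/SE | Rejection at nominal 5% |
|---|---|---|---|---|
| 0.2 | 0.25 | 0.05 | 0.15 | 5.2% |
| 0.2 | 0.5 | 0.10 | 0.30 | 6.0% |
| 0.3 | 0.5 | 0.15 | 0.44 | 7.3% |
| 0.4 | 0.5 | 0.20 | 0.59 | 9.1% |
| 0.5 | 0.5 | 0.25 | 0.74 | 11.4% |

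A noncentral t with 42 df gives 7.2% and 11.1% for the 0.15 and 0.25 SD rows, so the approximation is adequate.

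**What adjustment does to the SE.** Removing the part explained by education multiplies the SE by √(1 − r²): 0.339 falls to 0.332 at r = 0.2 and to 0.293 at r = 0.5. Imbalance takes some of this back. At d = 0.5 the multiplier is √(1 + (0.25/42)/(1/32 + 1/12)) = √1.052 = 1.026. The net factors are:
- r = 0.2: 0.980 × 1.026 = 1.005 (no gain);
- r = 0.3: 0.954 × 1.026 = 0.979 (about 2% smaller);
- r = 0.5: 0.866 × 1.026 = 0.889 (about 11% smaller).

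The case for adjusting is therefore mainly removal of bias; the gain in precision is small.

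**Chance imbalance.** With no systematic difference, the education means still differ by chance with an SD of 0.339. On the DSST scale that is 0.3 × 0.339 = 0.10 to 0.5 × 0.339 = 0.17 SD. This is already part of the nominal SE and is not additional error.

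**The case against.** The strongest reply is that an absent line in one list does not prove that the variable is absent from the data. Section 6.2.2 is headed as medical and psychiatric history and does not claim to be the whole CRF. The record review in 10.2.2 covers demographics without saying which, and the questionnaire and survey forms are in appendices that are not in the text. This stands. A reader might infer that the cognition contrast cannot be adjusted at all. The documents do not support that; they show only that no planned source of education is named.

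A reader might also infer that the report could not show which population was studied. That goes too far. Race and ethnicity are on the list and HIV status is documented; only the education and socioeconomic part lacks a variable. Nor does section 2.2 rest the trial on education. The stated gap is that SHUTi is untested in people with HIV, and education appears within one example alongside race, socioeconomic status and stigma.

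On size, both inputs are assumptions. The groups share all eligibility criteria except the ISI threshold and come largely from the same clinics, so a 0.5 SD difference in schooling is not a given, and at the low end the effect is negligible. The plan states p < 0.05 only for the ISI analysis (9.10), and 9.2 does not expect significant differences in either study. The rejection rates therefore describe a test that the plan has not specified. This too stands, and for that reason the shift itself is the more useful figure.

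Finally, sections 9.10 and 9.11 contain no Study II analysis, so listing education would not by itself yield an adjusted result. That is correct, and the fix has to cover both.

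**Conclusion.** The point holds as a gap in planned data collection that is cheap to close. The plan names no source of education or socioeconomic status, and one of its Study II primary outcomes is a single cross-sectional test score compared between groups that are neither randomised nor matched on schooling. The groups should not be described as balanced on age either, because only the 12 comparison participants have an age quota.

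Under the assumed ranges the shift is 0.05 to 0.25 SD. That is smaller than the random error of the contrast (SE 0.339 SD), but at the top it is half of a 0.5 SD effect. Section 9.2 says the pilot will be judged on clinically relevant effect sizes between the arms; if Study II is read in the same way, a shift of that size matters more than the change in error rate. The direction is unknown, because the documents do not say which group would have more schooling.

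The randomised ISI comparison in Study I is not confounded by this omission.

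**What to change.** 1. Add years of education completed to the 6.2.2 CRF list and, for description, one socioeconomic item, for all 44 participants. State that both are collected at the Entry Visit. The timing in 6.2.2 needs correcting in any case, because it refers to a Screening Visit that the Schedule of Events does not contain. If education is already captured on a form or from records, name that source instead.
2. Specify a Study II DSST comparison by ISI group, adjusted for age and education and reported beside the unadjusted difference, each with a confidence interval. Keep covariates to these few, because there are only 12 comparison participants. The argument here concerns DSST; it does not by itself justify the same covariate for CSRQ-25.
3. Report education by ISI group in a separate Study II baseline table, and by arm in the section 9.6 table. The 9.6 table alone is not enough: it covers the randomised intention-to-treat set and omits the 12 comparison participants.

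The cost is one or two questions at a visit that already takes place, and one degree of freedom for education in the DSST model. No new procedure or change in sample size is needed.

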### 6.2.3 Medication/Supplement Use and Psychiatric Treatment History

A medication history must be present in source documents. The following information will be recorded on the CRFs at the Screening Visit:

- Start dates of current antiretroviral treatments
- Start dates of current insomnia and antidepressant treatments
- Any other prescription medications within 30 days of Entry Visit
- Any supplements (non-prescription) used within 30 days of Entry Visit
- Previous psychiatric cognitive behavioral therapy treatments within one year of screening

### 6.2.4 Diagnoses/Updated Diagnoses

All confirmed and probable new diagnoses will be recorded on the CRFs, including current status at the time of the study visit.

### 6.2.5 Updated Medications

All new and/or discontinued prescription medications (including insomnia and antidepressant medications) taken since the Entry Visit will be recorded on CRFs with start and stop dates.

### 6.2.6 Clinical Assessments

#### 6.2.6.1 Height

Height will be recorded on CRFs at the Entry Visit

#### 6.2.6.2 Weight

Weight will be recorded on CRFs at both Entry and the Week 10 Visit.

#### 6.2.6.3 Resting Blood Pressure

Blood pressure measurements will be recorded on the CRFs at Entry and the Week 10 Visit. Blood pressure measurements should be performed on the same arm throughout the study. The participant should first sit quietly for five minutes. With the elbow and forearm resting comfortably on a flat table, the blood pressure should then be measured. After two minutes, repeat blood pressure measurement in the same arm. After another two minutes, repeat blood pressure measurements again. Therefore, three blood pressure measurements are to be documented in the CRFs.

#### 6.2.6.4 Resting Heart rate

Resting heart rate measurements will be recorded on the CRFs at the Entry Visit and Week 10 Visit. This may be done prior to the first blood pressure measurement. The participant should first sit quietly for five minutes prior to measurement of heart rate.

#### 6.2.6.5 Laboratories obtained through routine clinical care

No laboratories will be obtained as part of this study. Rather, the most recent laboratories obtained as part of clinical care will be abstracted and recorded on CRFs. These include most recently obtained CD4 cell count (absolute count and percentage), HIV-1 RNA level, hepatitis C antibody status (positive, negative), hemoglobin, glucose, albumin, creatinine, and estimated GFR (per CKD-EPI equation). The most recent HIV-1 RNA level must have been obtained within 90 days prior to the Entry Visit.

#### 6.2.6.6 Questionnaires

The ISI, PSQI, PHQ-9, SF-36, WHOQOL-HIV, PANAS, GAD-7, CSRQ-25, alcohol, tobacco, and substance use questionnaires (see Appendices) will be completed using online versions at both Study Visits in a quiet, private environment and assisted as needed by a trained member of the study team.

#### 6.2.6.7 Sleep History and Belief Surveys

More detailed histories of the participants' sleep histories and their beliefs about their sleep habits will be obtained using these Surveys. The PRE-Treatment Survey will be used for participants in both Studies I and II; the POST-Treatment Survey will be used only for those enrolled into Study I at the Week 10 Visit.

